Budget impact analyses (BIA). Utilizing a similar approach across projects, we will perform BIA to frame affordability to the VHA.⁷³ We will calculate the budget impacts of the clinical programs and compare them to each program's value. Value will be defined in light of all of the evaluation evidence. For example, value may be framed as total budget impact per unit gain in patient function or as total budget impact compared to the clinical team's narrative on how a program benefited patients. We will also consider framing budgetary impact against different domains, such as total costs by site or costs per Veteran participant. The clinical program leads will work with the implementation core to develop appropriate comparisons.

For the BIA we will consider three cost categories: (1) program-related implementation costs; (2) implementation strategy costs; and (3) resource utilization costs. We will not consider the fixed labor costs of implementation planning (e.g. stakeholder committee time) because these are one-time costs that would not occur if the clinical programs were implemented nationally. First, for **program-related costs**, we will measure personnel time and labor costs associated with preparing for and delivering the clinical programs using micro-costing. Clinical program trainer time and clinical delivery team time (including donated FTE) will be collected through personnel time logs and periodic time studies. Personnel time will be valued using VA Human Resources salary data. In addition to labor costs, we will consider program-related capital costs such as purchased durable equipment (e.g., walkers, measuring wheels, stop watches and portable pulse oximeters). Second, we will track **implementation strategy costs**, which includes REP and CONNECT training time, training materials, and site-visit travel. Travel costs will be measured using accepted per diem reimbursement, and the cost of personnel time will be measured as described above. Third, for **resource utilization costs** we will examine patient-level utilization pre-and post-clinical program by treatment and control subjects, to understand marginal costs/savings associated with the clinical programs.

Depending on the evaluation results of implementation Projects 1 and 2, the BIA will particularly focus on comparing total costs by the implementation method of REP vs. REP + CONNECT. Since CONNECT is expected to be more time-intensive and expensive than REP, it is critical to consider the relative gains (if any) to both team function and patient outcomes from adding CONNECT training to REP. For these projects we will also consider variability in budgetary impact by site (e.g. costs may differ by low versus high penetration sites or by team composition). Thus, we will examine costs by different measures of context at each site.

Implementation Products and Dissemination. The development and evaluation of strategies to build and support team readiness for implementation is a unique departure from currently funded QUERI program projects and this focus promises to make significant contributions to the field of implementation science. Mapping implementation techniques to team-based constructs will inform our development of a Team Building and Readiness Toolkit for Implementation that provides guidance to practitioners on tailoring implementation strategies to care teams within local settings. Also ultimately, discoveries from our implementation of clinical programs for vulnerable Veterans at high risk for disability will be valuable to VHA for realizing priority goals of improving patient access to care, supporting employee engagement, and creating a culture of high performance; thus synthesis and dissemination of our findings in the manner most useful to VHA is a high program priority. The Durham COIN has developed dissemination strategies based upon prior experience with conception, implementation, and reporting of innovations in VA healthcare delivery; we will build on this collective experience to inform strategies for Function QUERI dissemination activities. Stakeholders play a key role in maximizing Function QUERI's value and impact. Stakeholders will have direct involvement in and across projects, setting the stage for rapid, wide-spread acceptance and dissemination throughout VHA clinical practice. In addition to traditional strategies for

disseminating findings, Function QUERI will provide two types of products based on project activities and evaluations.

Clinical Program Implementation Packages. Clinical program packages will be developed and refined throughout the duration of each Function QUERI project. Findings from our evaluations of the clinical impacts of STRIDE, Group PT for Knee OA, and iHI-FIVES programs' packages will prompt further refinement at the conclusion of each project. Packages will include information including: provider training manuals/materials, information sheets for referring providers to facilitate consults to the program, lessons learned, suggested administrative strategies (e.g., scheduling), strategies to promote referrals and patient/caregiver adherence to program curricula, forms/templates for documenting patient status and outcomes, recommended exercises/lecture materials, templates for clinical assessments, patient educational materials and instructions. In close collaboration with our national operational partners, polished Clinical Program Implementation Packages will be developed and disseminated to guide program implementation efforts at other VA facilities.

Team Building and Readiness Toolkit, Function QUERI will serve a unique opportunity to evaluate the value of CONNECT for enhancing implementation efforts. A shortcoming in the field of implementation science is that implementation strategies are often not specified with sufficient detail for others to replicate them in research or practice. We will translate implementation findings across the 3 projects to identify the contextual factors and components from CONNECT that improve team function and optimize effectiveness of implementation of VA clinical programs. Applying the recommended guidelines for specifying discrete implementation techniques to this synthesis,⁷⁴ we will develop a Team Building and Readiness Toolkit to prepare teams for uptake of new clinical programs. Function QUERI personnel with relevant experience in toolkit development ([name], [name], [name]) will work closely with investigators to synthesize project findings and develop format and content for the drafted toolkit. Revisions and refinement of the toolkit will occur through two stages of review from our expert panels (Sections 2.7.2 and 2.7.3) to ensure the toolkit is readable, comprehensive, and meets the needs of the intended audiences. We will work closely with QUERI and our operational partners to ensure presentation and dissemination of the Team Building and Readiness Toolkit to all relevant audiences in VA Central Office in the final year of Function QUERI. We will also present results at annual research and dissemination and implementation science meetings and selected online portals such as the VA QUERI webinar series. VA Pulse Implementation Research Group and the VHA CommSite. Last, we will present our findings in relevant publication venues.

Management and Partnerships

Key Personnel

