Penetration will be measured using caregiver-level and provider-level measures at each site. *Caregiver-level*. We will measure penetration of the program at each site by assessing the number of caregivers "reached" by iHI-FIVES in a 6-month interval out of the total number of caregivers "eligible" during the same interval. *Provider-level*. Penetration at the provider-level will be measured as the number of providers who refer caregivers to participate in iHI-FIVES in a 6-month interval out of the total providers involved in caregiver support. *Site level*. Penetration at the site-level will be measured as the number of caregivers registered into the Caregiver Application Tracker (CAT) out of the number registered in the prior 6-months.

Fidelity will be measured as follows: 1) the number of 6-month intervals in post-implementation in which a site delivered at least two rounds of iHI-FIVES trainings out of the total number of 6-month intervals in post-implementation; 2) the number of rounds of training in which the full iHI-FIVES core curriculum topics were covered out of the total number of rounds of training offered.

These data will be obtained from review of electronic medical records via VistaWeb or Joint Legacy Viewer JLV, CDW data pull of health factor data, training records and attendance logs for each site, POC-reported data on instructors involved, and caregiver participant interviews.

Patient Outcome: Our primary individual-level outcome for iHI-FIVES is a patient-level outcome. Veteran **independence** (i.e., days spent alive and at home over the 6-month outcome period). This will be calculated as 180 days after the data pull date for that specific 6-month interval minus the total number of days **in an Emergency Department (ED) setting, an inpatient setting, or in a post-acute facility in the 6 months after the study start date (e.g., 6 months post-data pull).**

Caregiver Outcomes: Function. Our primary caregiver-level outcome of interest is **function** which includes depressive symptoms, as well as subjective **burden** (or the level of stress felt by CGs), and global **satisfaction** with VA health care quality measure as perceived by the caregiver. Caregiver outcome data will be obtained from surveys.

Patient data: Definition of the Primary Outcome

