Post-acute Facility days. We will also use admission and discharge dates to measure days in a post-acute facility setting. We will include Community Living Center, Community Nursing Home, and private or Medicare nursing home (e.g. not reimbursed by the VA) days directly following an inpatient stay. Specifically, a post-acute facility stay is defined as nursing home stay of 100 days or fewer immediately following discharge from an inpatient stay (on the same day or day before). For community-dwelling patients, if a patient has a long-stay nursing home stay following immediate discharge from the hospital, we will count the first 100 days as post-acute days and then thereafter the days will be censored. For patients who are identified as living in a nursing home (e.g. they have a nursing home stay for at least 101 days), being discharged from the hospital into a nursing home upon immediate discharge from the hospital will not be counted as post-acute care. This will be considered residential nursing home care and the days will not be included in the count of post-acute facility days. Chart review will confirm identification of community residence or nursing home residence if deemed necessary. We will cross reference against ED days and Inpatient Days to prevent double counting. If

a patient begins at a facility stay as a post-acute facility episode as defined above, but does not leave the facility by day 100, that is considered a transition to a 'residential nursing home stay'. Thus, the first 100 days of that post-acute episode will be counted as "100 days" not at home but then thereafter the patient will be censored.

Measures that will be created to help with censoring decisions:

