Residential Nursing Home Stays. A binary outcome of "any residential nursing home stay", defined as an episode of 101 or more days in a nursing home setting (CLC, CNH, VA and non-VA locations), will also be constructed and explored descriptively and as exploratory analysis. An episode of 101 days or more in our preliminary analysis of local GeriPACT patients and 100 HI-FIVES patients, pooled and not by arm, indicates a permanent move to a nursing home. We view this cut-off to help distinguish between post-acute skilled facility care and longer term residential custodial care. For comparison, in Medicare in 2016, mean length of stay for post-acute care was 30 days [32] and 97% of discharges from Medicare post-acute care facilities (SNFs) occurred by 90 days. Thus, it is likely that stays in a VA nursing home for less than 101 days can also be considered post-acute care and that days over this threshold will be considered residential. Additionally, since a "Residential Nursing Home Stay" represents a more permanent transition from the home environment, the patient will then be censored at the time of that transition from the primary outcome. Specifically, days after the admission date for a stay which lasted longer than 100 days will be removed from the "denominator" of the outcome, such that those days do not count as either at home or not at home because this measure is no longer considered applicable after the transition. In addition, for the rare cases in which patients living in a nursing home (e.g. they have a nursing home stay for at least 101 days) are then admitted and then discharged from the hospital back into a nursing home, these days following the discharge will also be counted as "residential nursing home days". We will examine the binary outcome of any residential nursing home stay as "the patient had a long stay nursing home stay ≥101 days in the 6 month outcome period across VA and VA-purchased stays" versus no long-stay nursing home stay.[33]

Finally, for descriptive purposes, the team will define other utilization types: any adult day health care use, any respite care, and any short-term nursing home stays will also be described. A short-term custodial nursing home stay, which is one that is 1) not within one day of an inpatient discharge and 2) less than or equal to 60 days, is not counted as a day not at home and patients will not be censored. This will be examined in descriptive analyses.

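### The iHI-FIVES primary outcome has no single scoring rule for death, for nursing-home stays over 100 days after hospital, or for censored days

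*Combined protocol and SAP*

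**What the plan says.** The section on iHI-FIVES program-specific methods (Patient Outcome) names the outcome "days spent alive and at home over the 6-month outcome period". The formula follows: "This will be calculated as 180 days after the data pull date for that specific 6-month interval minus the total number of days" spent in emergency care, on an inpatient ward or in post-acute care.

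The paragraph on post-acute facility days deals with a community-dwelling patient who goes straight from hospital into a long nursing-home stay: "we will count the first 100 days as post-acute days and then thereafter the days will be censored". It repeats the rule for a patient still in the facility at day 100: the first 100 days count as "not at home but then thereafter the patient will be censored".

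The paragraph on residential nursing home stays, defined as 101 days or more, says "the patient will then be censored at the time of that transition from the primary outcome". It then specifies that "days after the admission date for a stay which lasted longer than 100 days will be removed from the" outcome's denominator. The stated consequence is "such that those days do not count as either at home or not at home". The paragraph after it says that a custodial stay of 60 days or fewer, without a recent hospital discharge, "is not counted as a day not at home and patients will not be censored".

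The Aim 2b analysis section defines days at home as all days outside the emergency department, a nursing home or an inpatient ward. It sets a maximum of 180 for every patient, and obtains days not at home by subtracting each patient's days at home from 180. The candidate models are Poisson, negative binomial, their zero-inflated forms, and a two-part model. No offset or observed-days term is stated.

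**The concern.** An analyst who follows these sections in good faith cannot arrive at one score for certain Veterans.

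- **Death.** The label says alive, the formula has no term for death, and no iHI-FIVES section says how days after death are scored.
- **Long stays directly after hospital.** The post-acute paragraph counts 100 days and then censors. The admission-date sentence removes those 100 days, and it is not limited to stays entered from the community.
- **Censored days.** The nursing-home paragraph places them in neither state, but a subtraction from a fixed 180 has only two states. The Aim 2b wording also counts every nursing-home day as away from home, which conflicts with the zero score for short custodial stays.

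The score in question is the primary patient outcome. If the rule is chosen after outcomes have been seen, the choice depends on the data. The Impact section expects the program to avoid nursing-home placements, so the stays on which the text disagrees lie on a route by which the program is meant to work.

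**Working it through.** **The plan's own power figure.** The Sample size estimate section gives a mean of 8 days not at home, a 2-day reduction, variance equal to the mean, CV 0.3 to 0.5, 8 sites, 5 intervals, 400 Veterans and alpha 0.05 (two-sided assumed). I assume 2 sites cross at each of four steps, because the design figure is not readable. With 10 Veterans per site-interval, the Hussey and Hughes variance is

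I·s·(s + T·τ²) / [(I·U − W)·s + (U² + I·T·U − T·W − I·V)·τ²],

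where I = 8, T = 5, U = 20, W = 120, V = 60, s = 8/10 = 0.8 and τ = CV × 8.

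- CV 0.3: 6.4 × 29.6 / (32 + 691.2) = 0.262, SE 0.512, power 97.4%.
- CV 0.5: 6.4 × 80.8 / (32 + 1,920) = 0.265, SE 0.515, power 97.3%.

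The claim of at least 80% holds on the plan's inputs.

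**Death.** A Veteran with no facility use dies at home on day 5. By the formula, days at home = 180 − 0 = 180, and Aim 2b then gives 0 days not at home. By the label, at most 5 days are at home.

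**Long stay directly after hospital.** Two hypothetical Veterans:

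- A: hospital days 1–10, nursing home from day 11 to beyond day 180.
- B: home days 1–50, hospital days 51–60, nursing home from day 61 to beyond day 180.

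| Text followed | A: not at home / observed | A: 180 − not at home | B: not at home / observed | B: 180 − not at home |
|---|---|---|---|---|
| Post-acute paragraph | 110 / 110 | 70 | 110 / 160 | 70 |
| Admission-date sentence | about 10 / 10 | about 170 | about 10 / 60 | about 170 |
| Aim 2b wording | 180 / 180 | 0 | 130 / 180 | 50 |

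A was never at home and B was home for 50 days. The first two rows differ by 100 days whenever nursing-home admission falls on or before day 80, because 101 days then fit inside the window. For later admissions the gap is the number of days left. The 180 − not at home columns show where censored days go if the fixed 180 is kept: they become days at home.

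**Short custodial stay of 60 days.** The nursing-home paragraphs score 0 and the Aim 2b wording scores 60.

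**Size across the sample.** The plan gives no long-stay rate, so I assume 3%, stays like B's, and 8 of 180 days for everyone else. The section on caregiver enrollment gives a pool of 320 participating caregivers, against 15,000–18,000 Veterans. Half the site-intervals are post-implementation (U = 20 of 40), so about 7,500 of 15,000.

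- Long stays expected among 320 participants: 320 × 0.03 = 9.6.
- Averting all of them moves the rate by 9.6 / 7,500 = 0.128 percentage points, from 3% to 2.872%.
- Mean = 180 × [p·n + (1 − p)·8] / [p·o + (1 − p)·180], with n and o the days not at home and observed days for B.
- Post-acute paragraph (110, 160): 11.097 − 10.964 = 0.13 day.
- Admission-date sentence (10, 60): 8.224 − 8.215 = 0.01 day.
- Aim 2b wording (130, 180): 0.00128 × 122 = 0.16 day.

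With 18,000 Veterans the shifts are smaller.

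**Death across the sample.** If 90 days remain at death (an assumption), each 1-point difference in mortality between conditions adds 0.01 × 90 = 0.9 day under the literal formula. Two days would need 2/90 = 2.2 points, or 1.7 to 3.3 points for 120 to 60 days remaining.

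**The case against.** The outcome paragraphs can be read as one definition. Alive is in the label, so what is missing is a death rule; the plan never states an intention to credit the dead with days at home. The phrase about censoring at the transition fits the post-acute paragraph, which leaves one sentence out of line. The Aim 2b wording may be shorthand, and its 180 is worded as a maximum. Residential days are kept out of the primary outcome for a stated reason, and any residential stay is already a separate binary outcome for descriptive and exploratory analysis. Hospice referrals are excluded, which should reduce deaths.

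Much of this stands. It removes the inference that long-stay entry would go unreported. It does not supply a score. The formula, as the operational text, still has no death term. The admission-date sentence is worded for any stay over 100 days. Even with 180 as an upper bound, a subtraction made for each patient forces removed days into one of the two states.

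A reader might also infer that the choice of text could make or hide the whole 2-day target. If long-stay entry fell from 3% to 1% across all Veterans, the difference would indeed appear as 2.07, 0.15 or 2.44 days under the three texts. But 2% of 7,500 is 150 long stays averted, against about 10 expected among 320 participants of average risk. That scenario is illustrative only.

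**Conclusion.** Wrong as written. Stated rules give conflicting scores for the same Veteran, and for death the literal formula gives a score that contradicts its own label. The long-stay conflict reaches 100 scored days for one person and is confined to stays over 100 days that directly follow a hospital discharge. For long stays entered from the community the post-acute paragraph is silent, and the admission-date sentence can stand.

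The effect on the population mean is probably small: about 0.13, 0.01 or 0.16 day under the stated assumptions. These are a 3% long-stay rate, 320 as the total reach, average risk among participants and no spillover. The program targets higher-risk Veterans, so the shift could be several times larger and still fall short of 2 days. The documents do not support a claim of bias: that would need death or long-stay rates to differ between pre- and post-implementation, and no rates are given. Nor do they support a challenge to the stated power, which reproduces.

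**What to change.** 1. Change the formula under Patient Outcome so that days after the date of death are never credited as days at home. Pre-specify one handling (censor at death, or count as not at home), use the other as a sensitivity analysis, and report deaths by condition.
2. Restrict the admission-date sentence to long stays entered without a preceding hospital discharge and to patients already resident in a nursing home. Let the post-acute paragraph govern stays that directly follow hospital. Deleting the sentence would remove the only censoring start for long stays entered from the community.
3. Have Aim 2b refer to the component definitions, count days not at home directly, and replace the fixed 180 with observed days: a log offset in the count models, and a stated equivalent in each part of the two-part model.
4. Reconcile the start of the outcome window: the section defining the primary outcome uses the mid-point of each 6-month block, while Patient Outcome and Aim 2b use the data pull. Confirm the score for nursing-home stays of 61–100 days without a prior hospital discharge.

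The cost is text edits, a little programming and use of the date of death; no new patient contact is needed. If days after death are counted as not at home, the variance in the Sample size estimate section must be rechecked. With mortality m and uniform death times (assumptions), variance = 8 + m × 180²/3 − (90m)², which is 221, 528 or 1,007 at 2%, 5% or 10%. Power for 2 days at 15,000 Veterans would then be over 99%, 84% or 57–58%. Censoring at death avoids this.
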